5.5.4.2 Dose Management for CX-072

The following guidance is for dose modification of CX-072. Delays or permanent discontinuation of CX-072 may be required as outlined in [Table 10](#) and [Section 5.5.10](#). Dose reduction of CX-072 is not permitted. Guidance is adapted from American Society of Clinical Oncology Clinical Practice Guidelines ([Brahmer 2018](#)), which should be referenced for additional detail and information when assessing and managing AEs that are considered to be potentially immune related.

If, in the opinion of the Investigator, a toxicity is considered to be due solely to one component of the study treatment (ie, CX-2009 or CX-072) and the dose of that component is delayed, modified, or permanently discontinued in accordance with the guidelines in the Module, the other component may be administered if there is no contraindication.

Additional recommendations for interventions of irAEs depending on severity of the event are provided in [Section 5.5.5](#).

Table 10. CX-072 Dose Modifications for Select Adverse Events

Page 1 of 2

Adverse Event	Grade 1	Grade 2	Grade 3	Grade 4
Skin toxicities including dermatitis, Stevens-Johnson syndrome, or toxic epidermal necrolysis See also Section 5.5.5.11	No action; G1 does not apply to severe cutaneous toxicities (eg, Stevens-Johnson syndrome, toxic epidermal necrolysis, etc.).	Hold until recovery to ≤G1 or baseline.	Hold until recovery to ≤G1 or baseline. Consult with a dermatologist.	Permanently discontinue CX-072.
Colitis ^a See also Section 5.5.5.1	No action; may consider holding study treatment and resuming if toxicity does not exceed G1.	Hold until recovery to ≤G1.	Hold until recovery to ≤G1.	Permanently discontinue CX-072.
Increased serum transaminases (AST/ALT) or total bilirubin See also Section 5.5.5.2	No action; monitor laboratory values 1 to 2 times per week.	Hold until recovery to ≤G1 or baseline on prednisone ≤10 mg per day.	Permanently discontinue CX-072.	Permanently discontinue CX-072.
Pneumonitis See also Section 5.5.5.3	No action.	Hold until recovery to ≤G1.	Permanently discontinue CX-072.	Permanently discontinue CX-072.
Hypothyroidism or hyperthyroidism See also Section 5.5.5.4	No action.	Hold until recovery to ≤G1 or baseline (with hormone replacement for hypothyroidism).	Hold until recovery to ≤G1 or baseline (with hormone replacement for hypothyroidism).	Permanently discontinue study treatment.
Adrenal insufficiency See also Section 5.5.5.6	Consider holding until subject is stabilized.	Hold until recovery to ≤G1 or baseline with hormone replacement.	Hold until recovery to ≤G1 or baseline with hormone replacement.	Refer to endocrinologist. Hold CX 072 and contact Sponsor Medical Monitor to discuss discontinuation of study.
Hypophysitis See also Section 5.5.5.8	Consider holding CX-072 until stabilized on replacement therapy.	Hold until recovery to ≤G1 or baseline with hormone replacement.	Hold until recovery to ≤G1 or baseline with hormone replacement.	Refer to endocrinologist. Hold CX 072 and contact Sponsor Medical Monitor to discuss discontinuation of study.
Type 1 diabetes See also Section 5.5.5.7	NA; G1 does not apply to subjects with evidence of Type 1 diabetes or ketosis.	Hold until recovery to ≤G1 or baseline. Urgent endocrine consultation for all subjects. Initiate insulin therapy for all subjects.	Hold until recovery to ≤G1 or baseline. Urgent endocrine consultation for all subjects. Initiate insulin therapy for all subjects.	Refer to endocrinologist. Hold CX 072 and contact Sponsor Medical Monitor to discuss discontinuation of study.
Creatinine	No action; consider holding treatment pending workup.	Hold until recovery to ≤G1 or baseline. Consult nephrology.	Hold until recovery to ≤G1 or baseline. Permanently discontinue for Grade 3 nephritis.	Permanently discontinue CX-072.

Table 10. CX-072 Dose Modifications for Select Adverse Events

Page 2 of 2

Adverse Event	Grade 1	Grade 2	Grade 3	Grade 4
Pancreatitis (as diagnosed by biopsy, clinical examination, or symptoms); clinically asymptomatic elevation in amylase and lipase are not sufficient	Monitor for symptoms and laboratory abnormalities.	Hold until recovery to ≤G1 or baseline.	Hold until recovery to ≤G1 or baseline.	Permanently discontinue CX-072.
Myocarditis See also Section 5.5.5.5	NA		For any clinical suspicion, refer to cardiologist for workup, diagnosis, and treatment. Obtain cardiac MRI. Hold CX-072 and contact Sponsor Medical Monitor to discuss discontinuation of study.	
Encephalitis or meningoencephalitis See also Section 5.5.5.10	For any clinical suspicion, refer to neurologist for workup, diagnosis, and treatment. Hold CX-072 and contact Sponsor Medical Monitor to discuss discontinuation of CX-072.			
Ocular inflammatory toxicity (eg, uveitis, conjunctivitis, orbital inflammation, episcleritis) See also Section 5.5.5.9	Refer to ophthalmology.	Hold until recovery to ≤G1 or baseline. Refer to ophthalmology.	Permanently discontinue CX-072. Refer to ophthalmology.	Permanently discontinue CX-072. Refer to ophthalmology.
Guillain-Barre syndrome or myasthenia gravis	For any clinical suspicion, refer to neurologist for workup, diagnosis, and treatment. Hold study treatment and contact Sponsor Medical Monitor to discuss discontinuation of study treatment. For any confirmed diagnosis of any grade, treatment must be discontinued.			
Other immune-related adverse reactions (except those listed above) See also Section 5.5.5.12	No action.	No action; consider holding treatment depending on organs involved.	Hold and contact Sponsor Medical Monitor to discuss treatment, which may include administration of systemic steroids.	Hold and contact Sponsor Medical Monitor to discuss treatment, which may include administration of systemic steroids.
Grade 3 adverse reactions (except those listed above)	NA	NA	Hold until recovery to ≤G1 or baseline.	NA
Life-threatening or Grade 4 adverse reactions (except those listed above)	NA	NA	NA	Permanently discontinue CX-072.

^a Based on CTCAE for diarrhea as most often used clinically.

ALT = alanine aminotransferase; AST = aspartate aminotransferase; CTCAE = Common Terminology Criteria for Adverse Event; G1 = Grade 1; MRI = magnetic resonance tomography; NA = not applicable; PD-L1 = programmed death ligand 1.

Resume CX-072 in patients whose adverse reactions recover to Grade ≤1 or baseline, at the discretion of the Investigator unless otherwise stated in Table 10 and/or Section 5.5.5.12.

5.5.5 CX-072 Management of Immune-related Toxicity

All AEs should be monitored and managed according to standard of care. Refer to “Management of irAEs in patients treated with ICI therapy: American Society of Clinical Oncology clinical practice guideline” (Brahmer 2018) for specific guidance. For any suspected immune-related toxicities, other causes should be excluded and treated appropriately per standard of care.

5.5.5.1 Immune-related Colitis

Counsel subject to inform the Investigator of any abdominal pain, nausea, cramping, blood or mucus in stool or changes in bowel habits, fever, abdominal distention, obstipation, or constipation.

For Grade 1 events, consider temporary withholding CX-072 to confirm toxicity does not exceed Grade 1. Withhold CX-072 for Grade 2 or 3 immune-related colitis. For moderate (Grade 2) colitis administer corticosteroids, unless diarrhea is transient, starting with initial dose of 1 mg/kg per day prednisone or equivalent. Gastroenterology should be consulted. For severe (Grade 3) or life-threatening (Grade 4) colitis, administer corticosteroids at a dose of 1 to 2 mg/kg per day prednisone equivalents (for Grade 3) or 1 to 2 mg/kg per day methylprednisolone equivalents (for Grade 4) followed by corticosteroid taper. If Grade 3 symptoms persist for ≥ 3 to 5 days or recur after improvement, consider administering IV corticosteroid or noncorticosteroid (eg, infliximab). Consider colonoscopy/GI endoscopy in cases where subjects have been on immunosuppression and may be at risk for opportunistic infections as an independent cause for diarrhea (ie, cytomegalovirus [CMV] colitis) and for those who are anti-TNF or corticosteroid refractory. When symptoms improve to \leq Grade 1, taper corticosteroids over at least 4 to 6 weeks before resuming treatment, although resuming treatment while on low-dose corticosteroid may also be an option after an evaluation of the risks and benefits. Permanently discontinue CX-072 for Grade 4 or recurrent colitis upon restarting CX-072.

5.5.5.2 Immune-related Hepatitis

Monitor subjects for abnormal liver tests prior to and periodically during treatment with CX-072. (This management guideline may be altered for subjects with evidence of liver metastases who had screening elevation of transaminases; optimal subject management in these subjects should be discussed with the Medical Monitor).

For Grade 1 elevations of AST, ALT, and/or total bilirubin, monitor laboratory values 1 to 2 times per week. For Grade 2 elevations of AST, ALT, and/or total bilirubin (AST or ALT >3.0 to $\leq 5 \times$ ULN and/or total bilirubin >1.5 to $\leq 3 \times$ ULN), hold CX-072, recheck laboratory values and increase frequency of monitoring to every 3 days; administer corticosteroid 0.5 to 1 mg/kg per day (prednisone or equivalent) if the abnormal elevation persists with significant clinical symptoms in 3 to 5 days. CX-072 may be resumed only when symptoms improve to \leq Grade 1 and corticosteroid dose is ≤ 10 mg per day. Taper over at least 1 month. Subjects should be advised to stop unnecessary medications and any known hepatotoxic drugs. For Grade 3 hepatitis (AST or ALT $5-20 \times$ ULN and/or total bilirubin $3-10 \times$ ULN), immediately start corticosteroid 1 to 2 mg/kg per day methylprednisolone or equivalent. Increase frequency of monitoring to every 1 to 2 days. If corticosteroid refractory or no improvement after 3 days, consider mycophenolate mofetil or azathioprine (if using azathioprine, test for thiopurine

methyltransferase deficiency). Measure laboratory parameters at least daily or every other day; consider inpatient monitoring for subjects with AST/ALT $>8 \times$ ULN and/or elevated total bilirubin $3 \times$ ULN. Corticosteroid taper can be attempted around 4 to 6 weeks; re-escalate if needed; optimal duration unclear. For Grade 4 hepatitis, administer 2 mg/kg per day methylprednisolone equivalents and follow guidance for Grade 3.

Permanently discontinue CX-072 for Grade 3 or Grade 4 immune-related hepatitis (for subjects with elevation of liver transaminases at screening, discontinuation of CX-072 should be discussed with the Medical Monitor).

Infliximab might not be the most appropriate treatment option in the situation of immune-related hepatitis given the potential risk of idiosyncratic liver failure, mycophenolate mofetil may be considered.

5.5.5.3 Immune-related Pneumonitis

Monitor subjects for signs and symptoms of pneumonitis. Subjects with Grade 1 pneumonitis should be monitored weekly and CX-072 should be held if there is radiographic evidence of pneumonitis progression. CX-072 may be resumed with radiographic evidence of improvement or resolution. If no improvement, should treat as Grade 2. Subjects should be monitored weekly. For Grade 2 pneumonitis, recommend treatment with corticosteroids at a dose of 1 to 2 mg/kg per day prednisone equivalents, followed by a corticosteroid taper by 5 to 10 mg per week over 4 to 6 weeks. Consider bronchoscopy with bronchoalveolar lavage and empirical antibiotics. Monitor every 3 days. If no improvement after 48 to 72 hours of prednisone, treat as Grade 3. For Grade 3 pneumonitis, empirical antibiotics and corticosteroids (prednisolone IV 1 to 2 mg/kg per day) should be administered. If no improvement after 48 hours, may add 5 mg/kg infliximab or mycophenolate mofetil IV 1 g twice a day or IV immunoglobulin for 5 days or cyclophosphamide; taper corticosteroids over 4 to 6 weeks. Pulmonary and infectious disease consults should be sought if necessary. Subjects should be hospitalized for further management.

Withhold CX-072 for Grade 2 immune-related pneumonitis and permanently discontinue CX-072 for Grade 3 or 4 or recurrent pneumonitis upon restarting CX-072.

5.5.5.4 Immune-related Hypothyroidism and Hyperthyroidism

Monitor thyroid function prior to and periodically (test for thyroid-stimulating hormone [TSH] and free thyroxine (FT4) every 4 to 6 weeks and as clinically indicated) during treatment with CX-072.

For Grade 1 hypothyroidism, CX-072 may be continued with close follow-up and monitoring of TSH and FT4. For Grade 2 hypothyroidism, CX-072 should be withheld, thyroid hormone supplementation prescribed for symptomatic subjects with any degree of TSH elevation or in asymptomatic subjects with TSH levels that persist >10 mIU/L (measured 4 weeks apart). Endocrinology consult should be considered. For Grade 3 hypothyroidism, CX-072 should be

held, supplementation prescribed, and endocrinology consult obtained. For Grade 4 hypothyroidism, treatment should be permanently discontinued, supplementation prescribed, and endocrinology consult obtained. May admit for IV therapy if signs of myxedema (bradycardia, hypothermia).

For Grade 1 hyperthyroidism, may continue CX-072 with close follow-up and monitoring of TSH and FT4 every 2 to 3 weeks until it is clear whether there will be persistent hyperthyroidism. For Grade 2 hyperthyroidism, CX-072 should be held, medical management initiated, and endocrinology consultation considered. For persistent hyperthyroidism (>6 weeks) or clinical suspicion, a workup for Graves' Disease should be initiated. For Grade 3 hyperthyroidism, CX-072 should be held, medical management initiated, and endocrinology consulted. For Grade 4 hyperthyroidism, treatment should be permanently discontinued, supplementation prescribed, and endocrinology consult obtained. For severe symptoms or concern for thyroid storm, should hospitalize subject and initiate prednisone 1 to 2 mg/kg per day or equivalent tapered over 1 to 2 weeks. May also use saturated solution of potassium iodide or thionamide (methimazole or propylthiouracil).

Consider that thyroiditis is transient and within weeks resolves to primary hypothyroidism or normal. Graves' disease is generally persistent and due to increased thyroid hormone production that can be treated with antithyroid medical therapy.

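### Protocol Section 5.5.5.4 tells sites to prescribe supplementation for Grade 4 hyperthyroidism, which is the hypothyroidism treatment

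*Protocol*

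**What the plan says.** Section 5.5.5.4 of the Protocol gives graded instructions for two opposite conditions, hypothyroidism and hyperthyroidism, in subjects receiving CX-072.

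For hypothyroidism, Grade 2 introduces the term at issue: "thyroid hormone supplementation prescribed for symptomatic subjects with any degree of TSH elevation", with a further rule for asymptomatic subjects whose TSH stays raised. Grade 3 shortens this to prescribing supplementation. Grade 4 reads: "For Grade 4 hypothyroidism, treatment should be permanently discontinued, supplementation prescribed, and endocrinology consult obtained".

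For hyperthyroidism, Grade 2 calls for holding CX-072, starting medical management and considering an endocrinology consult. Grade 3 is similar: "For Grade 3 hyperthyroidism, CX-072 should be held, medical management initiated, and endocrinology consulted". Grade 4 then reads: "For Grade 4 hyperthyroidism, treatment should be permanently discontinued, supplementation prescribed, and endocrinology consult obtained". The next sentences cover severe symptoms or suspected thyroid storm: hospital admission, prednisone, and optionally potassium iodide or a thionamide. The section closes by noting that Graves' disease can be treated with antithyroid drugs.

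Two other places bear on how the section is used. Section 5.5.4.2 describes the content of Section 5.5.5 as "Additional recommendations for interventions of irAEs depending on severity of the event". The opening of Section 5.5.5 sets a general rule, "All AEs should be monitored and managed according to standard of care", and refers the reader to a published clinical practice guideline.

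**The concern.** Hyperthyroidism is an excess of thyroid hormone. Read with the section's own vocabulary, the Grade 4 sentence tells the site to add more. It is also the only hyperthyroidism instruction in the section that points this way.

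What is at stake is the correctness of a safety instruction at the highest non-fatal grade. Section 1 of the Protocol says the Module contains every guideline needed to manage subjects safely, so a site is entitled to take this text at face value. No endpoint, DLT rule, analysis population or sample size depends on it.

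**Working it through.** No statistical calculation applies to the wording. The check compares the instructions side by side and then counts the subjects to whom the sentence could have applied.

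**Step 1. The two ladders in Section 5.5.5.4 (paraphrased).**

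| Grade | Hypothyroidism | Hyperthyroidism |
|---|---|---|
| 1 | Continue CX-072, monitor | Continue CX-072, monitor |
| 2 | Hold; thyroid hormone under stated conditions; consider endocrinology | Hold; medical management; consider endocrinology |
| 3 | Hold; supplementation; endocrinology | Hold; medical management; endocrinology |
| 4 | Discontinue; supplementation; endocrinology | Discontinue; **supplementation**; endocrinology |

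The two columns differ in treatment at Grades 2 and 3 and become identical at Grade 4. The two Grade 4 sentences differ only in the name of the condition.

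**Step 2. What supplementation means here.** The section introduces it as thyroid hormone at Grade 2 hypothyroidism and uses the short form afterwards. Section 8.7 likewise uses the word in a hormonal sense when it defines immune-related events, although that passage concerns reporting and not treatment. Three other meanings were considered:

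- *Electrolytes.* Table 5 uses the word for correcting electrolyte abnormalities, but nothing in Section 5.5.5.4 concerns electrolytes.
- *Potassium iodide.* It is introduced separately, as an optional addition for severe symptoms or thyroid storm.
- *Hormone replacement later on.* The section notes that thyroiditis can resolve to hypothyroidism within weeks. That later state has its own graded instructions, and the disputed sentence is triggered by Grade 4 hyperthyroidism.

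None of these fits.

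**Step 3. Cross-check with Table 10 (Section 5.5.4.2).** The thyroid row covers both conditions. Its Grade 2 and Grade 3 cells restrict replacement with the words "with hormone replacement for hypothyroidism". Its Grade 4 cell says only to discontinue permanently. The table therefore supports the distinction at Grades 2 and 3, but at Grade 4 it neither supports nor corrects the sentence.

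**Step 4. Exposure.** CX-072 is given only in Parts D1, D2, E1 and E2. SAP Section 4.2 gives the treated subjects as 37 in Part A, 39 in Part A2, 10 in the mTPI-2 cohort, 3 in Part B and 10 in Part C1:

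37 + 39 + 10 + 3 + 10 = 99

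This equals the stated total of 99, so Parts D and E hold 99 − 99 = 0 subjects. SAP Section 8 separately says that nobody entered C2, D1 or D2; the zero for Part E follows from the sum. SAP Section 1 dates the end of enrollment to 07 July 2020.

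**The case against.** The strongest opposing case accepts the wording error and disputes its weight.

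First, no subject was exposed and enrollment has ended, so this could be called an editorial erratum. The count is correct, and it limits the consequence in this study to nil. It does not change what the instruction says.

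Second, the surrounding text largely covers the grade in question. The Protocol's generic severity scale (Table 11) treats Grade 4 as life-threatening and needing urgent intervention, so such a case would ordinarily also fall under the severe-symptom and thyroid storm guidance, which is appropriate. The disputed sentence itself requires an endocrinology consult, Section 5.5.5 invokes standard of care and a guideline, Section 5.5.4.2 labels the material as recommendations, and Sections 5.5.5.12 and 5.5.11 foresee refinement of toxicity management. All of this lowers the chance of harm. Yet it protects the subject only if the physician disregards one written instruction in favor of another.

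Third, the Grade 4 hyperthyroidism sentence does not itself say thyroid hormone. That is true: the meaning is inferred from the preceding paragraph. The inference is strong because the section offers no other kind of supplementation.

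Fourth, adding a clarification about antithyroid or symptomatic therapy would go beyond the Grade 2 and 3 wording. That is fair. The addition is optional and belongs to the medical monitor.

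**Conclusion.** The concern holds. The Grade 4 hyperthyroidism instruction is wrong as written and contradicts the guidance around it. It should be corrected.

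Its extent is one phrase, at one grade of one event, with no effect on any statistical quantity and no subject exposed in this study according to the SAP counts. The documents give no rate for Grade 4 hyperthyroidism, so no expected number of events can be stated. Two inferences underlie the conclusion: that supplementation carries the thyroid-hormone meaning the section gives it, and that the sentence was carried over from the hypothyroidism paragraph. The contradiction stands whether or not the second is right.

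**What to change.** In the Grade 4 hyperthyroidism sentence of Section 5.5.5.4, replace the supplementation phrase with the wording the paragraph already uses at Grades 2 and 3, so that it directs permanent discontinuation, initiation of medical management, and an endocrinology consult. A short parenthesis naming antithyroid or symptomatic therapy may be added if the medical monitor wants it. The medical monitor should confirm the final text.

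If Parts D or E were ever to enroll, sites should be told first. Otherwise the correction belongs in the next amendment, or at the latest before this CX-072 guidance is reused in another module. The separate CX-072 study, CTMX-M-072-001, which Protocol Section 1.5.2 describes as ongoing, is worth checking for the same sentence; these documents do not show whether it is there.

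The cost is one phrase. Endpoints, DLT rules, sample size and analyses are unchanged.

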5.5.5.5 Immune-related Myocarditis

Monitor subjects for myocarditis prior to and periodically during treatment with CX-072. For all grades of myocarditis, permanent CX-072 discontinuation should be discussed. Cardiology should be consulted, cardiac magnetic resonance imaging obtained, and high-dose corticosteroids should be administered (1 to 2 mg/kg of prednisone initiated rapidly (oral or IV depending on symptoms). In subjects without an immediate response to high-dose corticosteroids, consider cardiac transplant rejection doses of corticosteroids (methylprednisolone 1 g every day) and the addition of either mycophenolate, infliximab, or anti-thymocyte globulin. Permanently discontinue CX-072 for any >Grade 2 myocarditis.

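### For myocarditis above Grade 2, Section 5.5.5.5 orders CX-072 stopped for good, while Table 10 only holds and discusses; no text says which governs

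*Protocol*

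**What the plan says.** Four places in the Protocol bear on stopping CX-072 for myocarditis.

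- **Section 5.5.5.5** has two statements. One covers every grade: "For all grades of myocarditis, permanent CX-072 discontinuation should be discussed". The other is compulsory: "Permanently discontinue CX-072 for any >Grade 2 myocarditis".
- **Table 10 (Section 5.5.4.2), myocarditis row**, is triggered by suspicion: "For any clinical suspicion, refer to cardiologist for workup, diagnosis, and treatment". It continues: "Obtain cardiac MRI. Hold CX-072 and contact Sponsor Medical Monitor to discuss discontinuation of study". The row also points the reader to Section 5.5.5.5.
- **The sentence below Table 10** governs restart: "Resume CX-072 in patients whose adverse reactions recover to Grade ≤1 or baseline, at the discretion of the Investigator unless otherwise stated in Table 10". The full exception clause is "unless otherwise stated in Table 10 and/or Section 5.5.5.12".
- **Section 5.5.10** refers permanent discontinuation of CX-072 to Table 10. It then adds two criteria of its own: corticosteroids that cannot be tapered within 12 weeks, and Grade 2 or 3 treatment-related events that have not recovered within 12 weeks of the last dose.

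Section 5.5.4.2 names Table 10 and Section 5.5.10 as the places that set out delay and permanent discontinuation. It describes Section 5.5.5 as a source of further recommendations on treating immune-related events.

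**The concern.** A permanent stop for a potentially fatal event should read the same wherever a site looks it up. Here the narrative section makes the stop compulsory above Grade 2, while the dose-modification table, which a site is likely to open first, ends in a hold and a conversation. The object of that conversation also differs. The table speaks of leaving the study and the narrative speaks of CX-072. These are separate acts, because Section 5.5.4.2 allows the other drug to continue when a toxicity is judged due to one component only.

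At stake is whether a subject who has recovered from Grade 3 or 4 myocarditis may receive CX-072 again. Two sites, each following the Protocol in good faith, could answer differently.

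**Working it through.** No figure in the plan depends on this point, so the check is a comparison of texts. Take one case: myocarditis of Grade 3 or 4 that recovers to Grade 1 or baseline.

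**Route 1, Section 5.5.5.5.** The event is above Grade 2, so CX-072 ends permanently and recovery does not matter.

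**Route 2, Table 10 and the texts tied to it.**

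1. *Myocarditis row.* Withhold, refer, image, speak to the Medical Monitor. No cell prescribes a permanent stop. The extracted table leaves the row's column span unclear at the lower grades, but on either layout Grades 3 and 4 fall inside it.
2. *General Grade 4 row.* It prescribes a permanent stop only for events not already listed. Myocarditis is listed, so this row does not apply.
3. *Restart sentence.* The subject has recovered, so restart is at the Investigator's discretion unless a named exception applies. The named exceptions are Table 10 and Section 5.5.5.12. Table 10 states no bar for myocarditis, and Section 5.5.5.5 is not named.
4. *Section 5.5.10.* It returns to Table 10. Neither of its added criteria is met by recovery alone.

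Result: Route 1 forbids restart and Route 2 does not.

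**Is this just how the table is written?** Mostly not. For pneumonitis (Grades 3 and 4), hepatic events (Grades 3 and 4), ocular inflammation (Grades 3 and 4) and thyroid events (Grade 4), Table 10 carries the same permanent stop as the narrative. The row for Guillain-Barré syndrome and myasthenia gravis uses hold-and-contact wording close to that for myocarditis, then adds a compulsory stop once the diagnosis is confirmed. The myocarditis row has no such line.

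**Does it reach the dose-finding rules?**

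- *Grade 2.* Both texts call only for discontinuation to be discussed. The Table 5 entry that makes Grade 2 myocarditis a DLT when it forces CX-072 to stop therefore lies outside the disputed grades.
- *Grades 3 and 4.* Table 5 generally counts treatment-related events of these grades as DLTs, and its exceptions do not name myocarditis.
- *Six-week limit.* It counts interruptions as well as discontinuations.

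**Who was exposed?** CX-072 is given only in Parts D1, D2, E1 and E2. SAP Section 4.2 accounts for every treated subject: 37 (Part A) + 39 (Part A2) + 10 (mTPI-2 cohort) + 3 (Part B) + 10 (Part C1) = 99. This matches the total in SAP Section 8, and all of these are monotherapy parts.

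**The case against.** The strongest reply is that the two texts are successive steps. The table row is triggered by suspicion and covers work-up. It then points to Section 5.5.5.5, which supplies the rule once the event is graded. A site could obey both: hold and discuss, then stop if the grade exceeds 2. The encephalitis row looks similar, with hold-and-discuss in the table and the stop for a confirmed diagnosis only in the narrative. On this view the restart sentence reaches Section 5.5.5.5 through the table's cross-reference. Nor does the Investigator act alone, since the Medical Monitor must be contacted. Section 5.5.10 says only that Table 10 may require discontinuation, not that nothing else can.

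Much of this stands. The cross-reference and the Medical Monitor step are real, and the two-step reading is workable. But the Protocol does not state it. A pointer to another section does not give that section precedence, and a discussion does not bar restart. The restart sentence lists its exceptions expressly without Section 5.5.5.5. Where the drafters wanted a confirmed-diagnosis stop in the table, as for Guillain-Barré syndrome, they wrote one.

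A reader might also infer that the conflict alters dose escalation: one event reclassified in a cohort of three would move Figure 6 from stay (1 of 3) to escalate (0 of 3). The documents do not support this, for the reasons given in the check. The inference would need Table 5's Grade 3 list to be exhaustive, so that a quickly resolving Grade 3 myocarditis counted only if it forced CX-072 to stop. Table 5 introduces that list as examples included within Grade 3 events, so the narrower reading is not established.

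**Conclusion.** The inconsistency is real and confined to wording. For myocarditis above Grade 2, Section 5.5.5.5 requires a permanent stop of CX-072. Table 10, with the restart sentence and Section 5.5.10, does not, and nothing in the Protocol ranks one above the other.

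The consequence is for patient safety in Parts D1, D2, E1 and E2 only. No change to DLT counts, Figure 6 decisions or any planned analysis is shown. On the SAP's account no subject in this study was managed under either rule, which lowers the urgency but leaves the contradiction in the Protocol text.

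The conclusion rests on two assumptions: that the row's grade span includes Grades 3 and 4, and that no statement of precedence exists outside the documents supplied. It does not imply that either rule is clinically correct.

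**What to change.** The sponsor should reconcile the Table 10 myocarditis row, the restart sentence beneath it, Section 5.5.5.5 and Section 5.5.10, so that each grade of myocarditis has one CX-072 rule stated identically throughout. The reconciled text should say whether the decision concerns CX-072 or study participation, and whether suspected and confirmed disease are treated differently. The exception clause of the restart sentence should then match that rule. Which rule applies is a clinical decision for the sponsor and its medical advisers.

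The cost is Module wording in an amendment. No sample size, analysis or data collection changes.
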